Study Protocol

Official Title: A Pilot fMRI Study of TMS in Late-Life Severe Worry

ClinicalTrials.gov ID (NCT number): NCT03577106

Initial Protocol Date: 4/16/19

Last Protocol Update: 12/2/22

Scientific Background

Twenty percent of older adults in the community report severe worry. While worry is a universal human experience, severe and excessive worry in older adults has been recently linked to increased risk of stroke and other cardiovascular diseases, increased risk of conversion to Alzheimer's disease as well as to higher risk of all-cause mortality. As worry is a transdiagnostic construct, it is present in several mood and anxiety disorders, including major depressive disorder and generalized anxiety disorder. Current treatment choices in late-life (antidepressant/anxiolytic medications and psychotherapeutic interventions) have been proven moderately efficacious in reducing anxiety/depression burden, but ineffective in reducing worry severity, a phenomenon that may contribute to the high relapse rates associated with mood and anxiety disorders in the geriatric population. These elements support the need for novel, experimental interventions specifically designed to target the neural basis of severe worry in late-life. In our current research (R01 MH108509) we focus on describing the behavior of canonical neural networks during resting state and during worry induction in participants with low-to-high worry. Our research indicates that simple induction of worry activates a distinct set of regions (caudate/thalamus, visual cortex, dorsal anterior cingulate). Given the universality and potential evolutionary benefits of worry, we believe that the neural network associated with worry induction supports a normal, physiologic experience. However, the regions involved in maintaining worry (hippocampus, thalamus) as well as those associated with severe worry (orbitofrontal cortex, superior parietal gyrus, amygdala, parahippocampal gyrus) support a pathological phenomenon and may represent ideal targets for interventions.

Study Objectives

In this pilot proposal we intend to test the engagement of therapeutic targets during TBS. Based on our preliminary results, the most accessible and relevant target is the parietal cortex – a region that in our K23 sample remained significantly associated with severe worry after controlling for effects of comorbid depression or overall anxiety. As parietal cortex cerebrovascular flow increased in association with worry severity, we propose to use inhibitory TBS [high frequency TMS at 1 Hz] to modulate cortical plasticity and consequently reduce worry severity. To test target engagement, we will use the in-scanner worry induction paradigm designed by [name] and her mentors during her K23 award and currently use to probe worry induction in the R01 MH108509. Given the exploratory nature of this proposal and based on our preliminary data, we will use two measures of target engagement: 1) the relative decrease in BOLD signal in the parietal cortex and 2) the relative decrease in rSPG-dACC functional connectivity.

Study Design & Methods

This is an experimental, cross-sectional study. The estimated total enrollment for this study is 40 participants. The primary endpoint of this study would be the participant reaching study completion. The secondary endpoints include the removal of a participant from the study for the following reasons: The investigators may remove someone from the study if we discover that s/he no longer meets study

eligibility (e.g., has a surgery involving a metallic implant), for non-compliance with the study protocol, or if the study is not believed to be in her/his best interest.

Members of [name] team will contact those who have participated in the parent protocol ("FINA" STUDY19050150) and have consented for contact for future studies (via the FINA consent form). Recruitment will take place either over the phone or in-person. In-person, this could occur at any of the visits associated with STUDY19050150 once it is determined that the participant has a qualifying PSWQ score.

A physician investigator who is also a co-investigator will review the consent form with the participant. This will occur either in person, via phone call, or via videoconference. The purpose of the research study, the procedures involved in the conduct of the study, potential risks and benefits, and the rights of study participants will be discussed with the potential subject prior to the attainment of written informed consent. Participants will be allowed as much time as they need to consider participation after the consent form is reviewed. They will be encouraged to voice any questions or concerns at that time, prior to signing the consent form. Participants will be able to ask the physician investigator clarifying questions either in person, or via phone call, prior to signing the consent form. Subjects will be provided with a clear explanation of the objectives, procedures, risks and benefits of the study and all questions will be answered. A Physician Investigator of the study will then obtain consent. All members of our research team who have contact with potential participants will receive training in the importance of not coercing or otherwise unfairly influencing individuals to participate in this study. Participants will also be informed that signing the consent form does not bind them to complete any part of the study—they can always change their mind. Participants will sign the consent form prior to beginning any screening procedures (excluding the phone screen), clinical assessments, sleep and activity monitoring, TMS, or MRI scan as these require completed written informed consent.

Transcranial Magnetic Stimulation Protocol. Theta Burst Stimulation (TBS) will be targeted to the Inferior Parietal Cortex based on neural navigation software. TBS will be delivered for about 5-6 minutes, five days a week for two weeks, for a total of ten sessions. Accounting for set-up time and possible technical issues, participants will be informed that visits may last up to 45 minutes, but on average will take about 20 minutes.

The following measures will be administered both before and after the TMS intervention:

- 1) Penn State Worry Questionnaire (PSWQ)
- 2) Montgomery-Asberg Depression Rating Scale (MADRS)
- 3) Hamilton Anxiety Rating Scale (HARS) Sleep and Physical Activity Monitoring

As an optional component of the study, participants will be asked to complete a sleep diary and possibly wear an actigraphy monitor, depending on availability of the actiwatch, for at least 4 days prior to and throughout the TMS intervention. This is to determine their in-and-out of bed times, sleep onset, wake times, and how these may change during the TMS intervention.

The MRI scan will take place within 2 weeks of completion of the TMS sessions and will last approximately 1 hour. Scanning will be conducted on a 3 Tesla Siemens PRISMA scanner located in the MR Research Center at the University of Pittsburgh, using a 32-channel head coil (the same scanner and coil that is used for the current R01 study). We will gather functional MRI data (during rest and task) and structural MRI data including gray-matter volumetric estimates from T1-weighted images, white matter

hyperintensity volume (WMH) estimated from T2-FLAIR images and white matter microstructure integrity estimates from diffusion tensor imaging (DTI).

Functional MRI: The fMRI acquisition includes a 10-minute resting state acquisition (eyes open) followed by the worry induction task. We have chosen to use a 10-min acquisition as recent data has showed that the reliability is improved by increasing the scan length from 5 to 10 minutes. T2*-weighted BOLD-contrast functional image acquisition will use multiband (acceleration of 3) gradient-echo echoplanar imaging (EPI): TR/TE = 1800ms/30ms, Matrix= 96x96 with 60 slices, Voxel size = 2.5x2.5x2.5 mm³, parallel to AC-PC. The most inferior functional scan will be inferior to the most inferior aspect of the temporal lobes.

Additionally, a follow-up call will be made 1 month following their last TMS session. The 1-month follow-up call will include a general assessment of well-being and potential adverse reactions, along with over the phone administration of the HARS and MADRS. Research staff will send a copy of the Penn State Worry Questionnaire either via a link using Pitt RedCap or mail (including a postage-paid envelope) for the participant to complete and return.

Eligibility Criteria

Participants must have completed [name] study R01MH108509/STUDY19050150 and have a Penn State Worry Questionnaire score of 55 or above. Participants must be 50 years or older.

Participants must not meet any of the following exclusion criteria:

- 1) Any form of psychosis or Bipolar Disorder, dementia, or a history of substance abuse within the last six months
- 2) Use of antidepressants within the last five to fourteen days (adequate washout interval to be determined by the PI based on each specific antidepressant). For fluoxetine, the washout interval will be six weeks. However, for participants who are prescribed low dose psychotropics for pain, sleep disturbances, and/or medical conditions (e.g. amitriptyline for peripheral neuropathy, low dose trazodone as a sleep aid), these will be allowed in most circumstances. We will include participants on certain dosages of the most commonly prescribed antidepressants (for medical reasons) as follows: amitriptyline up to 50 mg/d, doxepin up to 50 mg/d, trazodone up to 100 mg/d, and imipramine up to 50 mg/d. We will review other cases individually and the PI will decide if the participants are eligible for the study and if they may continue the current medication.
- 3) Unable to complete MRI scans: presence of ferromagnetic metal in the body, claustrophobia
- 4) Contraindications for TMS:
 - a. Presence of a neurologic disorder or medical condition known to alter seizure threshold (e.g., stroke, aneurysm, brain surgery, structural brain lesion, brain injury, frequent/severe headaches)
 - b. Recurrent seizures or epilepsy in participant
 - c. Pregnancy
 - d. Metallic implants in body located at 30 cm or less from the position of the magnetic coil; presence in the body of other devices that may be affected by magnetic field (e.g. pacemakers).

5) Unable to temporarily discontinue benzodiazepines 48 hours prior to MRI scan. Participants on high doses of benzodiazepines (e.g., greater than or equivalent to 2 mg of lorazepam) will be excluded, given the complexity and potential complications of benzodiazepine taper/withdrawal.

Statistical Considerations

This is a pilot study aiming to explore neural signatures of treatment response. It is not statistically powered. Repeated measures ANOVA analysis for responders vs. non-responders using T2- T1 differences in BOLD changes across MRI task conditions (rest/worry induction) in the region of interest (parietal cortex). Response = decrease of 30% in PSWQ. Repeated measures ANOVA, correlation, and regression will be used to test changes in sleep patterns and their association with anxiety and fMRI response. Analysis of Structural MRI We will collect measures of gray matter volume (MPRAGE), WMH load (T2- weighted FLAIR), and white matter micro-structural integrity (DTI). These methods include assessment of regional gray matter volume using Automatic Labeling Pathway (ALP), regional WMH volume, and tract-based spatial statistics (TBSS) estimates of fractional anisotropy (FA) for the WM tracts. Regional WMH volumes: The automated WMH segmentation method is an iterative algorithm that automatically selects 'seeds' of WMH lesions and applies fuzzy connectedness to segment WMH lesions around the seeds (8). Using an automated method, the segmented WMH voxels are localized to the different white matter tracts defined on the Johns Hopkins University (JHU) White Matter Atlas (9). The same atlas used for localizing the WMH volumes is also used for generating tract-specific DTI measures. The DTI data is first preprocessed using tract-based spatial statistics. DTI summary measures are then generated using a 4-tissue class model, which treats normal appearing white matter as distinct from WMH. The other 2 classes (gray matter and CSF) are included to ensure accurate segmentation, but are not part of the planned analyses for this study. The global WMH burden and FA will be included as primary variables in Aim 3. As described above, we will also extract regional DTI and WMH measures for all white matter tracts. Secondary analyses will explore the role of tract-specific white matter alterations in tracts associated with emotion regulation (e.g. uncinate fasciculus, cingulum bundle). Analysis of functional MRI Our primary analyses of the BOLD-contrast fMRI dataset will follow an ROI approach that has been optimized by our group for analyzing fMRI in the elderly. We will also perform full-brain voxelwise secondary analyses. All standard processing steps are done in SPM8 [<http://www.fil.ion.ucl.ac.uk/spm/software/spm8>]. Additional custom software for alignment of elderly brain MRI's will also be used.

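### The BOLD-response analysis compares PSWQ responders with non-responders without using the MADRS and HARS, so a difference may reflect baseline mood or concurrent mood change rather than worry

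*Combined protocol and SAP*

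**What the plan says.** **Rationale.** Scientific Background describes worry as transdiagnostic: "it is present in several mood and anxiety disorders, including major depressive disorder and generalized anxiety disorder". It says current treatments reduce anxiety and depression but not worry, and calls for "novel, experimental interventions specifically designed to target the neural basis of severe worry in late-life". Study Objectives states that "the most accessible and relevant target is the parietal cortex" and adds that in the K23 sample this region's association with severe worry persisted "after controlling for effects of comorbid depression or overall anxiety".

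**Data.** Study Design & Methods lists the PSWQ, MADRS and HARS under the line "The following measures will be administered both before and after the TMS intervention". The one-month call repeats the two mood and anxiety scales, "along with over the phone administration of the HARS and MADRS".

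**Analysis.** Statistical Considerations plans a "Repeated measures ANOVA analysis for responders vs. non-responders using T2- T1 differences in BOLD changes" in the parietal region of interest. Response is a 30% fall in PSWQ, with no condition on the other scales. No covariate is named. Neither MADRS nor HARS appears in that section, and depression is not mentioned there. Anxiety appears once, in the sleep analysis, without a named scale. The section describes the study as an unpowered pilot.

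**The concern.** Responder status is observed, not randomised. On the protocol's own account worry overlaps with depression and anxiety, so PSWQ responders may differ from non-responders in two ways that matter:

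- their mood and anxiety before TMS, if these predict how much BOLD changes;
- the amount by which mood and anxiety improve over the same two weeks.

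Either could produce a BOLD difference between the groups with no direct link to worry. The evidence for the target was an adjusted association; the trial's own analysis drops the adjustment, so the two cannot be compared like with like. At stake is how the neural signature of response can be read when the next study is planned.

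**Working it through.** The plan states no alpha, effect size, SD or derivation of N, so there is no figure to reproduce. From the documents come N = 40, the 30% PSWQ rule and the list of scales. Everything else here is assumed: the correlations, a responder share of 30% or 50%, two-sided 0.05, and all 40 participants having complete T1 and T2 data.

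**1. Spurious association.** Let a mood/anxiety score correlate r1 with PSWQ change and r2 with BOLD change, with no direct worry-BOLD link. The implied worry-BOLD correlation is r1 × r2. The last column is the share of 4,000 simulated trials in which the unadjusted responder comparison is significant; the two values are the lower and upper of the two responder shares.

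| r1 | r2 | r1 × r2 | Significant |
|---|---|---|---|
| 0.3 | 0.3 | 0.09 | 6.3%–6.8% |
| 0.3 | 0.5 | 0.15 | 10.8%–11.7% |
| 0.5 | 0.3 | 0.15 | 11.0%–11.4% |
| 0.5 | 0.5 | 0.25 | 21.1%–23.0% |
| 0.7 | 0.3 | 0.21 | 17.3%–17.5% |
| 0.7 | 0.5 | 0.35 | 36.9%–41.9% |

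With that score as a covariate, the rate is 4.6% to 5.8% throughout.

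**2. Which covariate is needed.** If baseline mood is the driver, adjusting for the pre-TMS values restores about 5%. If concurrent mood change is the driver, it does not. Take continuous PSWQ change as predictor, r2 = 0.5, and mood change correlating 0.3 or 0.5 with baseline mood:

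- r1 = 0.5: 34%–36% unadjusted, 23%–29% after baseline adjustment;
- r1 = 0.7: about 62% unadjusted, 44%–55% after baseline adjustment;
- with mood change as covariate: about 5%.

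A continuous predictor is more sensitive to a confounded association as well as to a real one: at 0.5/0.5 the rate is 34%–36%, against 21%–23% for the responder split. Baseline adjustment alone is therefore not a specificity check.

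**3. Cost in precision.** The unadjusted two-group model leaves 40 − 2 = 38 df (critical t 2.024). Three baseline covariates leave 40 − 5 = 35 (critical t 2.030). The SE is multiplied by 1/√(1 − R²), where R² is the share of the predictor's variance that the covariates explain, less whatever BOLD variance they remove:

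- R² = 0.10: 1/√0.90 = 1.054; R² = 0.20: 1/√0.80 = 1.118;
- one covariate at r = 0.3: 1/√0.91 = 1.05; at 0.5: 1/√0.75 = 1.15; at 0.7: 1/√0.51 = 1.40.

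**4. Power if the effect truly runs through worry** (assumed correlation 0.5 with BOLD change):

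- responder split, unadjusted: about 69%–76%;
- responder split with baseline covariates: 53%–71%;
- continuous PSWQ change with the three baseline covariates: 83%–90% (baseline mood correlating 0 to 0.45 with PSWQ change);
- responder split with mood change as covariate: 62%–68%, 50%–57% and 32%–37% at worry-mood correlations of 0.3, 0.5 and 0.7.

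**5. Scale of what N = 40 can show.** The smallest standardised difference with 80% power is (1.96 + 0.842) × √(1/n1 + 1/n2): 0.89 for 20 versus 20 and 0.97 for 12 versus 28.

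**The case against.** The strongest reply is that the plan never poses a worry-specific hypothesis. Its stated aims are target engagement and exploration of neural signatures of response. The adjusted K23 association explains the choice of site, and accessibility was a reason too. This stands. A reader might infer that the trial fails to answer a question it set itself; the documents do not support that, since specificity is only implied by the rationale.

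Second, a reader might infer that adjustment would let the trial show a worry-specific effect of TMS. It would not. No control arm is described, and MADRS and HARS change are themselves post-treatment. Because worry is shared across mood and anxiety disorders, adjusting for those changes may also remove part of a real effect.

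Third, T2 − T1 differences already cancel stable additive differences between people. This is correct: baseline mood confounds only if it predicts BOLD change, and the documents give no figure for that.

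Fourth, covariates are expensive at N = 40. This stands in part. The three degrees of freedom cost almost nothing, but the SE inflation in the change-adjusted model can be large. For the baseline-adjusted model, replacing the responder split with continuous PSWQ change more than repays the loss.

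One limit on the data: the protocol places the scales before and after TMS and the described scan within two weeks of completing TMS. It does not show that scales and scans fall on the same visit.

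**Conclusion.** The omission is real. As written, a BOLD difference between PSWQ responders and non-responders cannot be separated from baseline mood severity or from concurrent improvement in mood and anxiety. The false-positive rate could lie anywhere from near nominal (6%) to 42%, depending wholly on assumed correlations of 0.3 to 0.7 and 0.3 to 0.5 and on 40 complete pairs.

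This limits interpretation; it does not invalidate an unpowered pilot. Adjustment is worth adding because the data are already collected and the planned estimate can stay. It is necessary for any comment on specificity, but not sufficient for a claim of it.

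**What to change.** In Statistical Considerations:

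1. Regress T2 − T1 change in parietal BOLD (worry induction versus rest) on continuous PSWQ change, with pre-TMS PSWQ, MADRS and HARS as covariates. Fit the same model to rSPG-dACC connectivity change, the second engagement measure in Study Objectives.
2. Report the planned unadjusted responder comparison beside it.
3. Pre-specify one exploratory model that adds MADRS change and HARS change, labelled as the worry-specificity check, because the baseline model does not address concurrent mood change.
4. Give estimates with confidence intervals, and state that they are associational because there is no described control arm and change scores are post-treatment.

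Parts 1 and 3 belong together: the continuous predictor recovers precision, and the change model guards against its greater sensitivity to confounding.

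The change costs one paragraph of wording and no new data. The downside is three degrees of freedom in the baseline model, two more in the change model (40 − 7 = 33 left), and SE inflation that grows with the worry-mood correlation. The change-adjusted estimate may therefore be imprecise, and a null result from it should not be read as absence of a worry effect.

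### A before-versus-during change in sleep timing mixes any TBS effect with the visit schedule and the weekday/weekend mix

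*Combined protocol and SAP*

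**What the plan says.** Study Design & Methods, under Sleep and Physical Activity Monitoring, makes the sleep record voluntary: "As an optional component of the study, participants will be asked to complete a sleep diary and possibly wear an actigraphy monitor". The record runs "for at least 4 days prior to and throughout the TMS intervention". It captures times in and out of bed, sleep onset and wake time, and its stated purpose includes "how these may change during the TMS intervention".

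The Transcranial Magnetic Stimulation Protocol paragraph gives TBS "five days a week for two weeks, for a total of ten sessions". It does not name the days of the week or the time of day. Visits are short: "visits may last up to 45 minutes, but on average will take about 20 minutes".

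For PSWQ, MADRS and HARS the text is "The following measures will be administered both before and after the TMS intervention", with no day fixed for the post-TMS assessment. For imaging, "The MRI scan will take place within 2 weeks of completion of the TMS sessions". The 1-month contact repeats the scales and mentions no sleep record.

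Statistical Considerations will use repeated measures ANOVA, correlation and regression to "test changes in sleep patterns and their association with anxiety and fMRI response". It does not define the sleep-change variable and has no weekday/weekend or visit-day term. No sham or untreated group is described.

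**The concern.** Bed and wake times are the sleep measures that a daily appointment, or a different share of weekend days, can most directly move. Stimulation and the visit timetable start and stop together. The minimum baseline is too short to hold a full week, so its weekend share depends on the calendar. With no comparison group and no session-free record after treatment, a mean shift in sleep timing could come from the timetable, the calendar or TBS, and the recorded data cannot fully separate them.

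At stake is the reading of a secondary result. A shift of some tens of minutes could be reported as a sleep effect of TBS when it reflects which days were recorded. Nights after the last session that were not recorded cannot be recovered later.

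**Working it through.** The documents give no figure for sleep change, its SD or power, so there is nothing of the plan's own to reproduce beyond the session count: 5 × 2 = 10.

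**Inputs from the documents.** Baseline of at least 4 days; ten sessions, five days a week for two weeks; 40 participants as the upper limit for the optional sleep sample.

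**Assumptions, not in the documents.** Sessions run Monday to Friday from a Monday, with the baseline immediately before. Wake time is w minutes later on weekend days (60; range 30 to 90) and v minutes earlier on visit days (range 0 to 45).

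**Day mix**
- First to last session: 12 days, of which 10 are visit days (83%) and 2 are weekend days (17%).
- Minimum baseline: Thursday to Sunday, 2/4 = 50% weekend.
- Seven-day baseline: 2/7 = 29% weekend.

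**Apparent mean change in wake time with no TBS effect** (negative = earlier during TMS)

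change = −v × 10/12 + w × (2/12 − weekend share of baseline)

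| v | w | Baseline | Change (min) |
|---|---|---|---|
| 0 | 30 | 4 days | 30 × (0.167 − 0.50) = −10 |
| 0 | 60 | 4 days | 60 × (0.167 − 0.50) = −20 |
| 0 | 90 | 4 days | 90 × (0.167 − 0.50) = −30 |
| 0 | 60 | 7 days | 60 × (0.167 − 0.286) = −7 |
| 15 | 0 | any | −15 × 0.833 = −12.5 |
| 30 | 0 | any | −30 × 0.833 = −25 |
| 45 | 0 | any | −45 × 0.833 = −37.5 |
| 30 | 60 | 4 days | −25 − 20 = −45 |

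A longer baseline alone therefore reduces the weekend part (20 to 7 minutes at w = 60) but does not remove it. Comparing within day type removes it. A weekday-with-weekday contrast still carries the whole visit effect v, because under this schedule every weekday during TMS is a visit day. The two non-visit days fall on one weekend, too few to carry the result.

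**Chance of a significant mean change from a pure 25-minute schedule shift** (v = 30, w = 0; paired test, normal approximation, two-sided 0.05; SDs and n = 20 assumed)

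| n | SD 45 min | SD 60 min |
|---|---|---|
| 40 | 0.94 | 0.75 |
| 20 | 0.70 | 0.46 |

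**Associations.** Express the schedule shift in units of the SD of true sleep change, with k its SD across participants.
- Same shift in everyone (k = 0): a correlation of 0.40 stays 0.40.
- Shift varies independently of outcome: 0.40/√(1 + k²), which is 0.36 at k = 0.5 and 0.28 at k = 1.
- True correlation 0, but the shift correlates 0.3 with the outcome: 0.3k/√(1 + k²), which is 0.13 at k = 0.5 and 0.21 at k = 1.

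Simulation gave the same values. A false link needs the size of the shift to track the outcome.

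**The case against.** The strongest reply is that the record fits its own aim. The plan asks how sleep changes during the TMS course, records exactly that period, and nowhere says that a shift will be attributed to TBS. This stands as a reason to keep change during TMS as the planned outcome. It does not make that change interpretable as an effect of stimulation.

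Three stronger readings are tempting, and the documents do not support them.

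- **That visit-free days are compared with ten weekday clinic days.** The text says five days a week, not Monday to Friday. It does not say that baseline days are free of visits, and the recording period includes the non-visit days between the two treatment weeks. The contrast itself is undefined. Visits average about 20 minutes at no stated hour, so the size of v is unknown and could be small.
- **That the calendar could equally push wake time 10 minutes later.** A baseline with no weekend days set against 2 of 12 during TMS needs a gap between baseline and treatment that is not described. A Friday start does give a Monday-to-Thursday baseline, but ten weekday sessions then span 14 days with 4 weekend days (29%). At w = 60 that is 60 × 4/14 = 17 minutes later. The direction thus depends on the start day, which the plan leaves open.
- **That relating sleep during treatment to later anxiety and fMRI change is an error.** A predictor recorded before its outcome is legitimate. The gap may also be short: the scales have no stated delay and the scan may fall anywhere within two weeks. A shift common to all participants leaves the correlation unchanged.

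It is also fair that the component is optional and that the pilot is stated not to be powered.

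**Conclusion.** The concern holds for the mean change from before to during TMS. With no control group, no later sleep record and no day-type or visit-day term, that change mixes any TBS effect with the visit schedule and the weekday/weekend mix. Under a Monday start and the minimum baseline, the weekend mix alone gives about 20 minutes earlier waking (10 to 30 for an assumed weekend delay of 30 to 90 minutes). It would point the same way in every participant on that calendar and would not average out. A visit effect would add to it, but its size rests wholly on assumption.

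For the associations the threat is weaker and conditional: attenuation if the shift varies unrelated to outcome, and a false link only if it tracks outcome. No primary endpoint depends on the sleep data. This is a low-priority but cheap improvement.

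**What to change.** 1. Lengthen the baseline diary to 7 days, so that it holds a full week.
2. Keep change during TMS as the planned sleep outcome and define it in advance. Estimate it within day type (weekday with weekday, weekend with weekend) or with a weekday/weekend term. This also serves participants who have already finished, but removes only the weekend part of the bias, not the visit effect.
3. Continue the optional diary, and the actiwatch where supply allows, for 7 days after the last session. Do this whatever the scan date, and do not move the scan. Baseline and post-TMS periods then each hold 2/7 weekend days and no TMS sessions. Add post-TMS minus baseline change as a second sleep measure in the models with HARS and fMRI change. Because Eligibility Criteria requires that participants can interrupt benzodiazepines for the 48 hours before MRI, include a sensitivity analysis omitting those nights for benzodiazepine users.
4. Where no post-TMS record exists, limit the conclusion to sleep during the TMS course and do not attribute it to stimulation.

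The cost is a short protocol and analysis edit, about 3 more baseline and 7 more post-TMS days of an optional diary, and longer use of each actiwatch, which could reduce how many participants receive one. No extra visit is needed.

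### The one specified link between BOLD change and worry change cuts PSWQ at a 30% drop; if change is normal and the relation linear, this loses at least 36% of the information

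*Combined protocol and SAP*

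**What the plan says.** The Statistical Considerations section gives the aim as exploring the brain correlates of response to treatment, and says openly that the pilot is not powered. The specified analysis is "Repeated measures ANOVA analysis for responders vs. non-responders using T2- T1 differences in BOLD changes across MRI task conditions" in the parietal region of interest, and the grouping rule is "Response = decrease of 30% in PSWQ". No reason for 30% and no expected response rate are given.

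Correlation and regression appear once in that section: "Repeated measures ANOVA, correlation, and regression will be used to test changes in sleep patterns" and how those sleep changes relate to anxiety and to the fMRI response. The later text on ROI and voxelwise analyses names no PSWQ term.

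The Study Design & Methods section lists PSWQ first under "The following measures will be administered both before and after the TMS intervention", so a change score exists for everyone who completes both assessments. The same section gives the size: "The estimated total enrollment for this study is 40 participants". Under Eligibility Criteria, participants must "have a Penn State Worry Questionnaire score of 55 or above".

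**The concern.** A graded score is collected and then reduced to two groups before it meets the imaging data. A 29% drop is pooled with no drop at all, while 29% and 31% fall on opposite sides. For someone entering at the minimum score of 55, the cut is a fall of 16.5 points, so a 16-point fall counts the same as none.

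In an unpowered pilot the useful product is an estimate of how strongly BOLD change tracks worry change. Splitting the score makes that estimate less precise. With no expected response rate, the group sizes are unknown, and if few participants respond the comparison rests on a handful of people.

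**Working it through.** **Inputs from the documents:** the 30% cut (Statistical Considerations), about 40 participants (Study Design & Methods) and entry PSWQ of at least 55 (Eligibility Criteria). There is no stated power, alpha, effect size or response rate, so there is no figure of the plan's own to reproduce.

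**Assumptions:** response rate *p*, the distribution of percent PSWQ change, the true correlation *r* between PSWQ change and BOLD change, a linear relation, and a two-sided 0.05 test.

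**1. Cut at the entry minimum.** 0.30 × 55 = 16.5 points.

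**2. Information kept by the split, normal case.** Relative efficiency is the squared correlation between the score and its indicator: E = φ(z_p)² / [p(1−p)].

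| Response rate | E | Loss | 40 participants count as |
|---|---|---|---|
| 50% | 0.637 | 36% | 25.5 |
| 30% | 0.576 | 42% | 23.0 |
| 20% | 0.490 | 51% | 19.6 |
| 10% | 0.342 | 66% | 13.7 |

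Under normality E peaks at exactly 50% and is symmetric about it, so every other rate loses more. These are small-correlation limits. Using the ratio of noncentralities, [r²E/(1−r²E)] / [r²/(1−r²)], the loss at a 50% rate is about 38% at r = 0.3 and 43% at r = 0.5.

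**3. Other distributions, same linear relation.** Across uniform, t with 5 df, and gamma and exponential shapes skewed either way, the loss is 25–52% at a 50% rate, 36–70% at 30%, 35–80% at 20% and 41–90% at 10%. With a long tail towards large improvement, the smallest loss need not fall at 50%. For the exponential in that direction, E is 0.48 at 50% and 0.65 at 20%.

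**4. Simulated power, n = 40** (20,000 replicates, normal change; a group with fewer than 2 members counted as not significant).

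| r | Continuous | Split, 50% rate | Split, 30% | Split, 20% | Split, 10% |
|---|---|---|---|---|---|
| 0.30 | 48% | 32% | 29% | 25% | 18% |
| 0.45 | 85% | 65% | 59% | 52% | 36% |
| 0.60 | 99% | 91% | 88% | 80% | 59% |

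If fewer are analysed, at r = 0.45 and a 50% rate the figures are 73% continuous against 51% split at n = 30, and 54% against 36% at n = 20.

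**5. The baseline-adjusted model, simulated directly** (6,000 replicates, n = 40). Assumed: pre-TMS PSWQ normal with mean 60 and SD 8, truncated to 55–80; change SD 9; whole-number scores; response a 30% drop. At response rates of 50%, 29%, 19% and 9%, adjusted regression has power 46–47% at r = 0.30, 83–84% at r = 0.45 and 99% at r = 0.60. The responder t-test has 32%, 29%, 25% and 17% at r = 0.30; 65%, 59%, 50% and 35% at r = 0.45; and 92%, 87%, 78% and 55% at r = 0.60.

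**6. Very small responder group.** The chance of at most one responder among 40 is 0.9⁴⁰ + 40 × 0.1 × 0.9³⁹ = 8.0% at a 10% rate. At a 20% rate it is about 0.15%.

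**The case against.** The strongest reply is that every run above takes BOLD change as linear in PSWQ change, which favours the continuous score by construction. If BOLD change instead jumps at the 30% cut, the ordering reverses. At n = 40 and r = 0.45 with normal change, power is then 66% continuous against 86% split at a 50% response rate, and 39% against 78% at 10%. This result is correct, and it makes the direction of the loss conditional on a graded relation. But no section proposes a threshold at 30%. The Study Objectives section describes parietal blood flow rising with worry severity, which is a graded association.

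Other points on that side:

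- **The target is response.** The stated aim concerns treatment response, and a responder contrast expresses that directly. This is fair, and it is a reason to keep the contrast as a secondary result. It is not a reason to make it the only link to worry.
- **Silence is not exclusion.** The ROI and voxelwise analyses might include a PSWQ term. That is possible, but none is written; if one is intended, it should be stated.
- **The pilot claims no power.** This is true, so no stated figure fails. It does not justify discarding precision in data already collected.
- **The regression needs inputs the plan leaves open.** The MRI description covers one scan after TMS, does not say when T1 is, and makes rest a separate acquisition before the task. These gaps are real, but they affect the planned ANOVA equally.

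**Conclusion.** The concern holds. As written, BOLD change meets worry change only through a 30% responder split, although the continuous score is available. With normal change and a linear relation, the loss is about 36% at a 50% response rate and greater at any other rate. Across the other shapes and rates tried it runs from 25% to 90%. The arithmetic is firm; the actual loss in this trial cannot be known, because the documents give no response rate, distribution or correlation. This is an inefficiency in the central brain-behaviour analysis. It is not an invalid test or a failed power claim, but it is cheap to correct and should be corrected.

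**What to change.** In Statistical Considerations, make the main brain-behaviour analysis a linear regression of post-TMS PSWQ on the T2−T1 parietal ROI BOLD contrast (worry induction against rest), adjusted for pre-TMS PSWQ. State which scan is T1 and how the contrast is formed; the existing ANOVA needs this too. Report the slope with its 95% CI, a plot, and a check for non-linearity and influential points, for example Cook's distance with the slope refitted without flagged points. Keep the 30% response rate and the responder ANOVA as descriptive secondary results. Optionally, fit the same model to the second engagement measure, "the relative decrease in rSPG-dACC functional connectivity", as a secondary analysis.

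The cost is a short edit, with no new data, participants or burden. The downside is reliance on approximate linearity and sensitivity to leverage points at about 40 participants, which the plot and the non-linearity and influence checks are there to expose.
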